11.2 At site level

Significant violation of ICH GCP and all applicable laws, regulations and protocol procedure that compromises the ability to achieve the primary study objectives or compromises patient safety may lead to the affected site to be discontinued from study participation by to Sponsor.

11.3 At the study level

Sponsor reserves the right to temporarily suspend and to discontinue the study prior to inclusion of the intended number of patients but intends only to exercise this right for valid scientific or administrative reasons. After such a decision, the investigator must contact all participating patients as soon as possible. Patients already enrolled in the study should continue in the study as per protocol unless judged otherwise by Investigator.

All study materials must be collected and all the eCRFs completed to the greatest extent possible.

Recruitment may be temporarily suspended in the following situations:

- occurrence of unexpected fatal or life-threatening adverse reactions;
- emergence of severe drug reactions linked to a common cause/ risk factor at different sites

Patients already enrolled in the study should continue receiving emapalumab per protocol unless decided otherwise by the Investigator.

The suspension will allow for the analysis of the available data by the Sponsor.

After re-evaluation of benefit/risk, the sponsor may recommend any of the following:

- to resume recruitment without any change;
- to implement risk minimization measures that may require protocol amendment;
- to implement conditions for study termination, e.g., next occurrence of a particular serious drug reaction;
- to discontinue the study.

12 Dissemination and publication of results

Sobi will register the study by posting study information and post study results regardless of outcome on a publicly accessible website in accordance with applicable laws and regulations, e.g., on <http://www.chictr.org.cn/>, <http://www.chinadrugtrials.org.cn/> and www.clinicaltrials.gov. The results of this study will be published within 12 months of the end of study.

Sobi is committed to publishing study results in a complete, accurate, balanced, transparent, and timely manner. Sobi follows the principles of the International Committee of Medical Journal Editors (ICMJE) recommendations for the conduct, reporting, editing, and publication of scholarly work in medical journals including criteria for authorship [38].

### Modification History

Version	Version Date	Author	Description
1.0	05DEC2022		FINAL
2.0	24OCTC2023		FINAL Definition of Overall Response updated with an addition of modified Overall Response as supplementary analysis (for details refer to Section 6.8.2 and Section 6.12 ).
3.0	24JUN2025		FINAL General statistical consideration updated to account for situation where non-numeric values are entered for quantitative measurements (for details refer to Section 6.1 ). Method of Overall Response analysis updated to clarify from which visit should observation be used (for details refer to Section 6.8.2 ). Overall survival added in Secondary Analysis Supporting Secondary Objectives (for details refer to Section 6.2.2 and 6.8.2 ) AE listings added in planned adverse event analysis (for details refer to Section 6.10.1 ).
4.0	06AUG2025		FINAL Method of Ability to Reduce Glucocorticoids analysis updated (for details refer to Section 6.8.2 )

## Abbreviation

Abbreviation	Specification
AE	Adverse event
BP	Blood pressure
CRF	Case report form
CT	Computed tomography
DRM	Data review meeting
ECG	Electrocardiogram
EOS	End of study
EOT	End of treatment
IV	Intravenous
HLGT	High level group term
HLH	Hemophagocytic lymphohistiocytosis
HLT	High level term
HSCT	Hematopoietic stem cell transplant
MedDRA	Medical Dictionary for Regulatory Activities
MRI	Magnetic resonance imaging
pHLH	Primary hemophagocytic lymphohistiocytosis
PO	Per os
PT	Preferred term
Q1	1 st quartile
Q3	3 rd quartile
sADR	Serious adverse drug reaction
SAE	Serious adverse event
SD	Study day
SOC	System organ class
WHO-DD	World Health Organization Drug Dictionary

## 1. Introduction

This statistical analysis plan was drafted for the “*An Open Label, Single Arm, Multi-Centre, Post-authorization Study to Describe the Safety and Efficacy of Emapalumab for the Treatment of Primary Hemophagocytic Lymphohistiocytosis in Treatment Experienced Chinese Patients*” (protocol No.: Sobi.EMAPALUMAB-104) of *Swedish Orphan Biovitrum AB*. In this document, the contents and methods of statistical analysis will be described in detail.

This statistical analysis plan was based on protocol (version 2.0, 01Jun2022) and Case Report Form (CRF, version 1.0, 20Sep2022).

## 2. Study Design

This is an open-label, single-arm, multi-centre study to collect safety and efficacy data on emapalumab in treatment experienced male and female patients diagnosed with Primary hemophagocytic lymphohistiocytosis (pHLH). The study will be performed in China.

The study will recruit at least 10 patients, and up to 18 patients if enrolled within the recruitment period.

Patients should already have received conventional hemophagocytic lymphohistiocytosis (HLH) therapy (treatment experienced patients), without obtaining a satisfactory response according to the treating physician or having shown signs of intolerance to it.

[Figure 1](#) summarizes the study design.

The study is divided into three parts: screening, treatment period, and follow-up. Patients will be admitted to the unit the day before the first administration of the study drug (study day minus one, SD-1).

**Figure 1. Overview of the study design**

SCREENING	TREATMENT					FOLLOW-UP					
Day -14 to Visit 1	Visit 1 (SD 0)	Visit 2 (SD 3-4 and onwards) every 3-4 days	W8 Primary assessment timepoint if treatment continues	W9-onwards until start of conditioning for HSCT	EOT (3±1 day after last infusion)  Primary assessment timepoint if treatment stopped before week 8	Pre-HSCT		Post HSCT			
	Initial dose	Subsequent doses				Pre-conditioning	W 1/2/3	D 30	D 60	D 100	M6

Abbreviations SD, study day; EOT, end of treatment; HSCT, hematopoietic stem cell transplant; W, week; D, day after HSCT; M, month; EOS, end of study

The patient will enter screening after informed consent is obtained and will undergo screening assessments to confirm eligibility. Duration of the screening period will be kept as short as possible and should not exceed 2 weeks.

First emapalumab infusion, at a dose of 1 mg/kg, marks the start of the treatment period. The treatment period is foreseen to continue until start of conditioning for HSCT, if deemed indicated for this patient. Infusions will take place twice weekly, at a dose determined by the Investigator for each infusion. Emapalumab will be administered on the background of dexamethasone, which can be tapered or increased as needed. No wash-out is required prior to conditioning for HSCT. Last visit of the treatment period is the end of treatment, which occurs 3 days after the last infusion of emapalumab. Assessment of efficacy objectives occurs at end of treatment. After the start of conditioning for HSCT (or treatment completion, if HSCT is not deemed indicated), the patient proceeds to follow-up period. Follow-up visits are planned in relation to the date of the HSCT, or last emapalumab infusion (if HSCT is not deemed indicated). Duration of the follow-up is one year after HSCT, or after the last emapalumab infusion. The end of study visit (EOS) for each patient will occur at the latest 18 months from first dose of emapalumab.

Patient will be considered screened after informed consent is obtained.

For further details on the schedule of events for treatment period and follow-up period, please refer to Table 3 and Table 4 in study protocol.

### 3. Estimand

Objectives	Endpoints	Estimand
Primary Objective: To collect safety data on emapalumab in treatment-experienced Chinese pHLH patients	Primary Endpoint: Permanent discontinuation of study drug due to emapalumab-related adverse events as judged by the investigator	Estimand 1: Primary Estimand Target population: All patients received at least one infusion of IMP Treatment: Refer to Section 6.4 in study protocol Endpoints: Refer to the left column Strategies for addressing intercurrent events: The treatment policy strategy will be applied for the estimand Population-level summary: The number and percentage of patients who permanently discontinue study drug due to emapalumab-related adverse events
	Secondary Endpoint 1: Treatment-emergent adverse events (AEs)	Estimand 1.1 Target population: All patients received at least one infusion of IMP Treatment: Refer to Section 6.4 in study protocol Endpoints: Refer to the left column Strategies for addressing intercurrent events: The treatment policy strategy will be applied for the estimand Population-level summary: Incidence of treatment-emergent AEs
	Secondary Endpoint 2: Treatment-emergent serious adverse events (SAEs)	Estimand 1.2 Target population: All patients received at least one infusion of IMP Treatment: Refer to Section 6.4 in study protocol Endpoints: Refer to the left column Strategies for addressing intercurrent events: The treatment policy strategy will be applied for the estimand Population-level summary: Incidence of treatment-emergent SAEs (refer to Section 6.8)
	Secondary Endpoint 3:	Estimand 1.3

	
Treatment-emergent laboratory abnormalities
	
Target population: All patients received at least one infusion of IMP          Treatment: Refer to Section 6.4 in study protocol          Endpoints: Refer to the left column          Strategies for addressing intercurrent events:          The treatment policy strategy will be applied for the estimand          Population-level summary:          Incidence of treatment-emergent laboratory abnormalities (refer to Section 6.8)

	
Secondary Endpoint 4:          Treatment-emergent vital sign abnormalities
	
Estimand 1.4          Target population: All patients received at least one infusion of IMP          Treatment: Refer to Section 6.4 in study protocol          Endpoints: Refer to the left column          Strategies for addressing intercurrent events:          The treatment policy strategy will be applied for the estimand          Population-level summary:          Incidence of treatment-emergent vital sign abnormalities (refer to Section 6.8)

Secondary Objective:          To collect efficacy data on emapalumab in treatment-experienced Chinese pHLH patients
	
Secondary Endpoint 1:          Overall Response, i.e., achievement of either Complete or Partial Response or HLH Improvement, at EOT or Week 8 (whichever occurs earlier)
	
Estimand 2.1          Target population: All patients received at least one infusion of IMP          Treatment: Refer to Section 6.4 in study protocol          Endpoints: Refer to the left column          Strategies for addressing intercurrent events:          The treatment policy strategy will be applied for the estimand          Population-level summary:          The number and percentage of patients achieving overall response and each component of overall response at EOT or week 8 (whichever occurs earlier)

	
Secondary Endpoint 2:          Time to first Overall Response, i.e., time from the date of first dose of
	
Estimand 2.2          Target population: All patients received at least one infusion of IMP

[figure not shown]
	
emapalumab to the first achievement of response (Complete or Partial Response or HLH Improvement)
	
Treatment: Refer to Section 6.4 in study protocol          Endpoints: Refer to the left column          Strategies for addressing intercurrent events:          The treatment policy strategy will be applied for the estimand          Population-level summary:          Time to first response prior to HSCT will be estimated using Kaplan-Meier method

	
Secondary Endpoint 3:          Cumulative duration of response, i.e., total time in response from the first achievement of an Overall Response until EOT
	
Estimand 2.3          Target population: All patients received at least one infusion of IMP excluding those who do not achieve response at least once between the date of first dose and EOT          Treatment: Refer to Section 6.4 in study protocol          Endpoints: Refer to the left column          Strategies for addressing intercurrent events:          The treatment policy strategy will be applied for the estimand          Population-level summary:          Duration of response will be estimated using descriptive statistics

	
Secondary Endpoint 4:          Ability to reduce glucocorticoids by 50% or more of the baseline dose during emapalumab treatment
	
Estimand 2.4          Target population: All patients received at least one infusion of IMP          Treatment: Refer to Section 6.4 in study protocol          Endpoints: Refer to the left column          Strategies for addressing intercurrent events:          The treatment policy strategy will be applied for the estimand          Population-level summary:          Number and percentage of patients able to reduce glucocorticoids by 50% or more of the baseline dose during emapalumab treatment

	
Secondary Endpoint 5:          Investigator assessed response
	
Estimand 2.5          Target population: All patients received at least one infusion of IMP

		
Treatment: Refer to Section 6.4 in study protocol
 
Endpoints: Refer to the left column
 
Strategies for addressing intercurrent events:
 
The treatment policy strategy will be applied for the estimand
 
Population-level summary: Investigator’s assessment of clinical response up to HSCT will be estimated using descriptive statistics

	
Secondary Endpoint 6: Survival to start of HSCT conditioning, i.e., time from the date of first dose of Emapalumab to date of death, with censoring at conditioning for HSCT or at last date of contact for patients who did not undergo conditioning for HSCT
	
Estimand 2.6
 
Target population: All patients received at least one infusion of IMP
 
Treatment: Refer to Section 6.4 in study protocol
 
Endpoints: Refer to the left column
 
Strategies for addressing intercurrent events:
 
The treatment policy strategy will be applied for the estimand
 
Population-level summary: Survival to start of HSCT conditioning will be estimated using Kaplan-Meier method

	
Secondary Endpoint 7: Survival after HSCT, i.e., time from HSCT to death, with censoring time at last date of contact for patients with no event.
	
Estimand 2.7
 
Target population: All patients received at least one infusion of IMP and underwent HSCT
 
Treatment: Refer to Section 6.4 in study protocol
 
Endpoints: Refer to the left column
 
Strategies for addressing intercurrent events:
 
The treatment policy strategy will be applied for the estimand
 
Population-level summary: Survival after HSCT will be estimated using Kaplan-Meier method

**Secondary**

**Objective:**

To collect efficacy data on emapalumab in treatment-experienced Chinese pHLH patients

## 4. Sample Size Consideration

Sample size is not based on statistical considerations but the data from up to 18 Chinese patients will add sufficient information to the safety and efficacy profile established during the global clinical development program for emapalumab in pHLH patients.

## 5. Analysis Sets

### All screened analysis set

The All screened analysis set includes all patients who sign the informed consent/assent including screen failures. This population will be used only for the purpose of describing patient disposition and for protocol deviations (screen failures will be excluded in protocol deviation outputs).

### All treated analysis set

All treated analysis set comprises all patients who received at least one infusion of IMP.

## 6. Statistical Methods

### 6.1. General Statistical Consideration

All subjects-related safety and efficacy data collected will be included. Annotated or illustrative description records will only be included in the listings. Suitable tabular and graphical summaries will be prepared for individual data and for appropriate summary statistics, and all data shall be listed. In this study, subject number will be used as the unique identification of subjects in data listings.

All safety and efficacy analyses will be based on the all treated analysis set unless specified otherwise. If applicable, all endpoints will be summarized using descriptive statistics. For continuous variables, the descriptive statistics will include the number of observations, mean, standard deviation, median, first and third quartiles (Q1, Q3), minimum and maximum. For categorical variables, the descriptive statistics will include the number of observations and percentage for each category. Two-sided 95% confidence interval may also be calculated for certain efficacy endpoints.

For continuous laboratory test measurements (including hematology, biochemistry, coagulation, sCD25, CSF analysis, and urinalysis), round to 1 decimal place for minimum and maximum statistics, 2 decimal places for mean, median, Q1 and Q3, and 3 decimal places for standard deviation. For other continuous measurements, the number of decimal places for minimum and maximum statistics will be kept consistent with source data; mean, median, Q1 and Q3 will be rounded to one more decimal place than source data; standard deviation will be rounded to two more decimal places than source data. For survival analysis, round to 1 decimal place for median survival time (and Q1, Q3) and survival rate, and 2 decimal places for standard deviation and confidence limits. For categorical measurements, the calculated percentage for each categories will be rounded to 1 decimal place, confidence limits will be round to 2 decimal places.

No formal statistical hypothesis testing will be performed for this study.

All statistical analyses will be performed with statistical analysis software (SAS) System (SAS Institute, Cary, NC) version 9.4 or later.

Baseline will be defined as the last available measurement or recording prior to the first study drug administration. For assessments performed only on screening visit prior to the first emapalumab infusion, the measurement or the recording of the screening visit will be used as baseline. For

assessments that are also performed pre-infusion on visit 1 in addition to screening visit, the measurement or recording pre-infusion on visit 1 will be used. If the measurement or recording pre-infusion on visit 1 is not available, then the measurement or recording of the screening visit will be used.

Unless otherwise noted, descriptive statistical summary will only include data from scheduled visits or time points. Data from unscheduled visits or time points will be presented in data listings. For data of quantitative measurements but are collected with characters such as “>/≥” or “</≤”, the numeric part of the value will be used in the descriptive analysis. For other cases where characters are entered for quantitative measurements, the result will not be used in the descriptive analysis but only included in data listing.

If deemed necessary, specific data points may be excluded from the analysis based on related discussion in the data review meeting (DRM). The decisions and reason(s) for exclusion will be documented separately in Resolution of Data Review Meeting in detail.

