6.5.1.5 Unscheduled visits

Unplanned visits may occur anytime during the study should the patient need to be assessed or treated for any clinical condition that arises during the study. This includes the evaluation and follow-up of AEs and SAEs. Data collected during such a visit should be entered in the eCRF. An unscheduled visit should not affect the regular visit schedule and assessments.

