### Treatment-Emergent Laboratory Abnormalities

The treatment policy strategy will be applied for estimating the incidence of treatment-emergent laboratory abnormalities. Laboratory abnormalities recorded since receiving the first dose of investigational medication until EOS will be presented regardless of any potential intercurrent events. Laboratory abnormalities that are absent at baseline will be considered treatment-emergent.

The overall incidence of treatment-emergent laboratory abnormalities will be summarized at event level and subject level by test name (e.g. hematology, biochemistry, coagulation, sCD25, urinalysis, or cerebrospinal fluid analysis if applicable) and test item.

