### Treatment-Emergent Vital Sign Abnormalities

The treatment policy strategy will be applied for estimating the incidence of treatment-emergent vital sign abnormalities. Vital sign abnormalities recorded since receiving the first dose of investigational medication until EOS will be presented regardless of any potential intercurrent events. Vital sign abnormalities that are absent at baseline will be considered treatment-emergent.

The overall incidence of treatment-emergent vital sign abnormalities will be summarized at event level and subject level by test item.

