### **6.10.2. Laboratory Test Results**

Data on the test item(s), result, clinical significance, unit, normal range limits, and additional comments for hematology, biochemistry, coagulation, sCD25, urinalysis, and cerebrospinal fluid (CSF) analysis (if clinically indicated) will be documented in the CRF. Laboratory test data will be collected at all scheduled visits for the treatment period and the follow-up period.

The numeric findings of laboratory test result (including hematology, biochemistry, coagulation, sCD25, CSF analysis, and urinalysis) will be summarized for screening visit and following visits using descriptive statistics. Actual values and actual changes from baseline will be presented. Qualitative clinical evaluation (normal, not clinically significant, clinically significant, or not done) will be tabulated for screening visit and presented using shift table for following visits. CSF analysis will only be tabulated for subjects with available baseline CSF analysis results and available CSF results for at least one post-treatment visit.

Listings will be provided for all laboratory data collected for scheduled and unscheduled visits. In addition, all abnormal laboratory findings of subjects with normal result at baseline will be listed.

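### The SAP does not say whether laboratory and vital-sign abnormalities found at unscheduled visits count in the two incidence endpoints, and its default rule would leave them out

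*SAP*

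**What the plan says.** SAP 6.1 gives the general rule that, where nothing else is noted, "descriptive statistical summary will only include data from scheduled visits or time points". The next sentence says where the rest goes: "Data from unscheduled visits or time points will be presented in data listings". Earlier in the same section stands a broader statement: "All subjects-related safety and efficacy data collected will be included".

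SAP 6.8.1 defines the two endpoints. For laboratory results: "The overall incidence of treatment-emergent laboratory abnormalities will be summarized at event level and subject level by test name" and test item. For vital signs: "The overall incidence of treatment-emergent vital sign abnormalities will be summarized at event level and subject level by test item". In both, an abnormality is treatment-emergent if it was absent at baseline, and the window runs by date from the first dose to end of study. Neither paragraph mentions scheduled or unscheduled visits.

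Protocol 5.1.2 lists both as secondary endpoints supporting the primary objective. Protocol 6.5.1.5 explains why off-schedule data arise: "Unplanned visits may occur anytime during the study should the patient need to be assessed or treated for any clinical condition". It adds that such visits include the work-up of adverse events (AEs) and that their data are entered in the eCRF.

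SAP 6.10.2 covers unscheduled results in its listings: "Listings will be provided for all laboratory data collected for scheduled and unscheduled visits". SAP 6.10.4 does the same for vital signs.

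**The concern.** A scheduled-only rule suits by-visit means and shift tables, where each patient should contribute one value per planned visit. An incidence asks a different question: did the patient ever have the abnormality after the first dose? Leaving out off-schedule results can then only lower the count.

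The results left out are not a random sample either. Unscheduled visits take place because a patient needs assessment or treatment, so new abnormalities are more likely there than at a routine visit. The rule also covers time points within a visit. Extra blood pressure, heart rate or saturation readings taken while a reaction is being managed could be treated as unscheduled time points.

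At stake are the completeness of two pre-specified safety endpoints and their reproducibility. Two programmers working from the same SAP could select different records and report different incidences.

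**Working it through.** **No figure to reproduce.** The documents give no rate of unscheduled visits and no expected incidence. There is no hypothesis test (SAP 6.1), and the sample size has no statistical basis (SAP 4). The check is therefore a reading of the text, followed by a calculation of scale.

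**Step 1. Does the default reach these tables?** SAP 6.1 says that all endpoints are summarised descriptively where applicable, and that categorical variables get counts and percentages. An incidence table is such a summary, so the default applies unless something is noted otherwise.

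**Step 2. Is anything noted otherwise?**

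| Text | Points towards |
|---|---|
| SAP 6.1, scheduled-only default | exclusion |
| SAP 6.1, unscheduled data go to listings | exclusion |
| SAP 6.1, all collected safety data included | inclusion, but general |
| SAP 6.8.1, date window from first dose to end of study | inclusion, but silent on visit type |
| SAP 6.10.1, all AE records enter the analysis | explicit inclusion, for AEs only |
| SAP 6.10.2 and 6.10.4, unscheduled results named | listings only |

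The AE section states inclusion outright. The two abnormality endpoints have no such sentence. The text does not settle the matter, and a programmer who follows the specific rule in 6.1 would exclude.

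**Step 3. What would still be captured elsewhere?** Protocol 6.5.6.1 and 6.5.7 require clinically significant vital signs and laboratory values to be reported as AEs. These are analysed whatever the visit type. Three gaps remain:
- the endpoints in SAP 6.8.1 do not require clinical significance;
- Protocol 6.5.5.1.1 has the symptom recorded rather than the test result when an abnormal finding comes with symptoms, and 6.5.5.1.3 prefers a diagnosis to individual signs, so the abnormality may be tabulated under another term;
- a listing gives no incidence.

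**Step 4. Scale.** Protocol 6.1.1 plans n = 10 to 18 treated patients. One patient missed on a test item changes its subject-level incidence by 100/n points: 100/10 = 10.0, and 100/18 = 5.6.

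Going from no patient to one, with exact (Clopper-Pearson) 95% intervals:

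| n | Patient missed | Patient counted |
|---|---|---|
| 10 | 0/10 = 0% (0 to 30.8%) | 1/10 = 10.0% (0.3 to 44.5%) |
| 18 | 0/18 = 0% (0 to 18.5%) | 1/18 = 5.6% (0.1 to 27.3%) |

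**Step 5. How likely is at least one missed patient?** Let q be the share of patients whose only new abnormality on an item is recorded off schedule. The documents give no value, so the q values here are assumptions. P(at least one) = 1 − (1 − q)^n, and the expected number is nq.

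| q (assumed) | n = 10: probability, expected | n = 18: probability, expected |
|---|---|---|
| 5% | 40%, 0.5 | 60%, 0.9 |
| 10% | 65%, 1.0 | 85%, 1.8 |
| 20% | 89%, 2.0 | 98%, 3.6 |

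**The case against.** The strongest reply is that the SAP already includes these data. The default yields to anything noted otherwise, the endpoints set a window by date rather than by visit, and 6.1 says that all collected safety data are included. Record selection may also be fixed in the table shells and dataset specifications to which SAP 11 refers and which are not available here. This stands to the extent that a reader who infers a definite exclusion goes further than the text. It does not remove the problem, because the general sentence and the specific rule sit in the same section and nothing says which governs.

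The second reply is that little would be lost. Clinically significant abnormalities reach the AE tables. Listings show every off-schedule result, and abnormal findings in patients normal at baseline are listed as well. With at most 18 patients, these can be read one by one. During treatment, the main laboratory panels are repeated at twice-weekly visits, so many patients would be counted from a scheduled result anyway. Nothing is tested, and the primary endpoint is untouched. All of this limits the harm, but none of it supplies the missing count in the endpoint itself.

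A reader might also infer the size of the bias from the visit spacing, since after day 100 the only visits are at 6 months and 1 year. The documents do not support that step. Spacing gives the chance that one episode coincides with a scheduled visit. The loss due to this rule also needs the chance that the episode was recorded off schedule, which is unknown; an abnormality that nobody measured is missing under either rule. A per-episode chance also does not carry over to a subject-level endpoint, which needs only one new abnormal result.

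**Conclusion.** The point holds as a gap in specification with a known direction. Under the SAP 6.1 default, and with no exception stated in 6.8.1, new laboratory and vital-sign abnormalities seen only off schedule are omitted from two secondary safety endpoints, and their incidence is biased downwards. Under the other reading there is no omission. The SAP should say which applies.

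The size cannot be derived. The shift of 10 points (n = 10) or 5.6 points (n = 18) is per patient missed on an item, and the probabilities in the working rest on assumed values of q. The effect is probably smaller during treatment than late in follow-up, where scheduled visits are far apart.

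It would be wrong to conclude that safety signals are lost from the study. The AE analysis and the listings remain, and what is at risk is mainly abnormalities not captured as AEs. The change is worth making because the endpoints support the primary objective and the remedy is nearly free. It does not bear on the primary endpoint or the sample size.

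**What to change.** Add one sentence to SAP 6.8.1, under both headings: the incidence tables count every result after the first dose up to end of study, whether from a scheduled or an unscheduled visit or time point. State in 6.1 that this is an exception, and keep the scheduled-only rule for by-visit descriptive and shift tables.

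The subject-level count needs no further rule, since a patient counts once per item. If the event-level count is kept, define an event so that closer sampling of the same abnormality does not add events. SAP 6.8.1 gives no such definition now.

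The cost is a short text change and a different record selection for two tables. Reported incidences may rise, and they will depend somewhat on how often patients are sampled, so a footnote saying that unscheduled results are included would help the reader.
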